### 1.3 SCHEDULE OF ACTIVITIES

	Prior to enrollment Time 0; Day -1 (-30)	Clinic Visit Time 1; Day 1	Post-clinic Time 2; Day 1 (+10)	Time 3; Day 2 – Day 30	Time 4; Day 30 (+21)	Time 5; Day 120 ± 21	Time 6; Day 210 ± 21
Electronic Record Review	X						
Informed Consent	X						
'Opt-in' 4-week text message program	X						
Baseline Questionnaire (e.g., past EBT utilization, smoking behavior, mediators, moderators)	X						
Study brochure		X					
Randomization		X					
Control & Intervention Videos		X					
Text Messages-Control				X			
Text Message-Intervention				X	X	X	X
Outcome Evaluation							
Satisfaction with intervention/post video questionnaire			X				
Follow-up Questionnaires (e.g., mediators, self- reported EBT contact and utilization, quit attempts)					X	X	X
Objective confirmation of contact and utilization of EBT resources				X	X	X	X
Biochemical validation of self-reported smoking abstinence					X	X	X
Adverse Events Reporting		X	X	X	X	X	X

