### 6.3 MEASURES TO MINIMIZE BIAS: RANDOMIZATION AND BLINDING

We will conduct a stratified block randomization procedure with small, random size blocks. Participants will be randomized to one of two groups, Intervention or Control, after completing the baseline assessment, the in-clinic eligibility screener (to ensure that their smoking status has not changed since the screener), and receipt of brochure. Randomization will be stratified by motivation to quit (ready to quit smoking in 30 days vs. not ready to quit within 30 days). Only the PI, the project director, the statistician, and the clinic RAs (RAs who are setting up the video for each patient) will be unmasked to treatment condition. These RAs will not be involved in the collection of any outcome data. Because both the Intervention and Control groups will be watching a video, all dental providers will be able to be masked to participant's treatment condition. The RA who performs follow-ups and collection of saliva cotinine will be masked to treatment condition.

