## 9.2 SAMPLE SIZE DETERMINATION

Power calculations focus on the comparison of those randomized to the Intervention vs. Control on our primary outcome of any EBT engagement through a chi-square test at the two-sided  $\alpha = 0.05$  level. We will not adjust p-values for multiple comparisons.

Using the odds ratio as our effect size, we estimate the effect of the Intervention will be  $OR=2.05$  (corresponding to percent with any EBT utilization of 22.7% in the Control vs. 37.6% in the Intervention). Only two published studies tested the efficacy of an intervention on EBT utilization rate, both at 12-months follow-up. Brooks et al reported an EBT utilization rate (i.e., Quitline or clinic-based program) of 29.8% in the intervention group vs. 14.7% in controls ( $OR=2.4$ ). Fu et al reported an EBT utilization rate (counseling or medications) of 44.2% in the intervention and 30.6% in controls ( $OR=1.8$ ). Therefore, we use the average EBT utilization rate in the control groups from these studies (22.7%) as our ‘any EBT utilization’ rate under the null hypothesis in the power analysis. Because neither of the above studies used video or were conducted in a dental setting, we also considered previous studies testing the effectiveness of videos on cessation, which report ORs of 1.9 and 3.0, and previous studies on cessation in dental settings (meta-analysis  $OR=2.38$ ). Based on all the above, we conservatively chose an anticipated effect size of  $OR=2.05$  (corresponding to rates of 22.7% vs. 37.6%). With  $\alpha=0.05$  (two-sided), we need a total sample of  $n=300$  subjects to achieve 0.80 power of detecting this anticipated effect. However, because of potential differences between clinic sites, and assuming an attrition rate of 20% (lost to follow-up or ineligible post-randomization), in consultation with the NIDCR in April 2024 we received authorization to increase the sample size to  $n=455$  subjects ( $n=227$  for intervention and  $n=228$  for control group). Therefore, with  $\alpha=0.05$ , the anticipated effect size of  $OR=2.05$ , and 364 subjects (455 minus 20% lost to follow-up or ineligible post-randomization), we will have 0.87 power to detect the anticipated effect.

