### 9.4 STATISTICAL ANALYSES

#### 9.4.1 GENERAL APPROACH

For descriptive statistics, categorical data will be presented through percentages and continuous variables will be presented through means and standard deviations. For statistical tests, a two-tailed  $p$ -value less than 0.05 or a 95% confidence interval not including the null value will be used for statistical significance.

EBT utilization will be analyzed by computing a utilization index score (UIS). The UIS will be created by first computing a proportion of utilization score for each of the EBTs for each participant. For example, a participant who completed 4 of 5 quitline calls has a proportion score of 80. For NRT, the recommended length of treatment is 8 weeks and the proportion completed by each participant will be computed. For the NCI smoke-free text message program, the recommended length of participation is 56 days, and we will compute the proportion of days completed, as well as the proportion of text messages responded to (of those that required a response). For clinic-based programs, the proportion will be calculated as the number of sessions attended divided by maximum number of sessions offered at the corresponding clinic. Because participants may use one or more EBT programs, the overall “utilization index score” will be the sum of the above individual proportion scores of each EBT for each person. These individual scores will be summed to obtain the UIS (continuous variable). The distribution of our UIS will be examined for approximate normality, and transformations to improve normality or categorization of the index score will be considered if appropriate. For primary analyses, we will control for age, gender, and race/ethnicity, along with variables identified through preliminary analyses as significantly differing between study groups.

This study will be registered with Clinical Trials.gov prior to the start of participant enrollment.

A formal Statistical Analysis Plan (SAP) will be completed prior to the completion of the study and the unblinding of the study data.

---

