#### 9.4.2 ANALYSIS OF THE PRIMARY ENDPOINT(S)

Aim 1 Hypothesis 1.1. Between group differences in any EBT utilization. The outcome is any EBT utilization over the 7-month study period, including use of the Quitline, clinic-based programs, NCI’s text message program, nicotine replacement therapy, other evidence-based medication (e.g., Bupropion, Varenicline). Quitline use will be based on objective usage data provided by National Jewish Health (the operator of the state's quitline contracted by the Massachusetts Tobacco Cessation and Prevention Program) (e.g., whether contact was made, number of counseling calls, whether patients set a quit date, whether nicotine replacement was requested and delivered to patients), and engagement with NCI’s text message program use (e.g., whether patients opted into the program, response rates, length of time in the program) will be obtained objectively from the program. Data on other EBT utilization (clinic-based counseling; receipt of smoking cessation meds outside of the quitline) will be based on self-report. This binary outcome will be analyzed through a logistic regression model, with the intervention effect described through an odds ratio and 95% confidence interval. We will control for age, gender, race/ethnicity, and variables identified through preliminary analyses as significantly differing between study groups.

Aim 1 Hypothesis 1.2. Dose of EBT utilization. The outcome is our UIS (described in 9.4.1) which summarizes participation in one or more EBTs (the quitline, nicotine replacement or other medications, the NCI SmokefreeTXT program, and clinic based programs). Multiple linear regression will be used to compare the Intervention vs. Control, controlling for age, gender, race/ethnicity, and variables identified through preliminary analyses as significantly differing between study groups. The intervention effect will be described through the slope, representing the difference in mean UIS for those in the Intervention vs. Control group.

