#### 9.4.5 BASELINE DESCRIPTIVE STATISTICS

Baseline demographic and smoking-related characteristics will be compared for those randomized to the Intervention vs. Control groups. Because of randomization, we do not anticipate baseline differences between groups, but if significant differences are found, those variables will be considered as potential confounders in later analyses. Categorical characteristics will be described through percentages and compared across groups through chi-square tests, and continuous measures will be described through means and standard deviations and be compared through t-tests.

---

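### The primary and secondary models leave out the randomisation stratum (readiness to quit) and add covariates by baseline significance tests; the cost is modest inefficiency and a model that cannot be fixed in advance

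*Combined protocol and SAP*

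**What the plan says.** Section 6.3 (and 4.1) sets the design: "Randomization will be stratified by motivation to quit (ready to quit smoking in 30 days vs. not ready to quit within 30 days"). It is the only stratification factor; clinic site is not one.

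Section 9.4.2 gives the covariate rule for any EBT utilization: "We will control for age, gender, race/ethnicity, and variables identified through preliminary analyses as significantly differing between study groups". The same rule governs the linear model for the utilization index (9.4.1, 9.4.2). In 9.4.3 it also governs the Poisson model for number of EBTs, the logistic model for combined counseling and medication, and the mixed logistic models for quit attempts, motivation and verified abstinence. None of these names readiness, site or past EBT use. Readiness enters only the moderator interaction models (9.4.7, 9.4.9).

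Section 9.4.5 compares baseline variables between arms by chi-square and t-tests and adds that "if significant differences are found, those variables will be considered as potential confounders in later analyses". Under 9.4.1, significance is a two-tailed p-"value less than 0.05 or a 95% confidence interval not including the null value will be used for statistical significance".

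Two further variables are relevant. Section 9.2 explains the larger sample as needed "because of potential differences between clinic sites, and assuming an attrition rate of 20% (lost to follow-up or ineligible post-randomization"). Section 1.3 lists a "Baseline Questionnaire (e.g., past EBT utilization, smoking behavior, mediators, moderators"), so past EBT use is collected before randomisation.

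**The concern.** An analysis should normally reflect the factor used to restrict randomisation. If readiness predicts EBT use, stratifying removes its between-arm variation from the treatment comparison. A model without it still counts that variation in the standard error, so the test is conservative and some of the benefit of stratifying is lost.

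The selection rule does not repair this. It asks whether a variable differs between arms, which under randomisation is chance, rather than whether it predicts the outcome. A balanced, strongly prognostic variable is left out; an unimportant one that happens to differ is put in. The covariate list is then known only after arm-level data have been examined. The wording is also unsettled: 9.4.2 says such variables will be controlled for, while 9.4.5 says only that they will be considered.

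Motivation to quit is the sharpest case. The outcome in 9.4.3 is a yes/no question about quitting in the next 30 days, and the stratum is readiness to quit within 30 days. The mixed model uses the 1-, 3- and 6-month data and is described as testing changes in motivation, yet the baseline value enters neither as a covariate nor as an outcome.

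**Working it through.** **Inputs from the protocol.** Two-sided 0.05; 22.7% v 37.6% with any EBT use; 455 less 20% = 364 analysed, 182 per arm (9.2). Sections 2.1 and 3 put 40-80% of smokers as not ready to quit, so 20-60% ready.

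**Assumed, because the protocol gives no figure.** Prognostic odds ratios: readiness 1 to 6, site 1.3 to 1.5, past EBT use 2 to 3. The prevalence of past EBT use and the site split are also assumed.

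**1. The plan's own figures.** Odds ratio = (0.376/0.624)/(0.227/0.773) = 2.05. With difference 0.149 and pooled rate 0.3015:

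- null SE = √(2 × 0.3015 × 0.6985/182) = 0.0481
- alternative SE = √((0.227 × 0.773 + 0.376 × 0.624)/182) = 0.0475
- power = Φ((0.149 − 1.96 × 0.0481)/0.0475) = Φ(1.15) = 0.875

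The stated 0.87 reproduces. The same formula asks for 296 in total, against the plan's 300 "subjects to achieve 0.80 power of detecting this anticipated effect".

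**2. Omitting the stratum.** Trials of 182 per arm were simulated with 1:1 allocation within readiness strata and overall rates held at 22.7% and 37.6% (20,000 runs per setting). Ranges run over 20%, 40% and 60% ready.

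| Readiness OR | Power without | Power with | Gain | Type I without | Type I with |
|---|---|---|---|---|---|
| 1 | 0.871-0.877 | 0.871-0.877 | 0 | 0.047-0.050 | 0.047-0.051 |
| 2 | 0.873-0.878 | 0.878-0.886 | 0.005-0.008 | 0.046-0.049 | 0.049-0.050 |
| 3 | 0.878-0.881 | 0.891-0.896 | 0.012-0.015 | 0.041-0.045 | 0.047-0.050 |
| 4 | 0.880-0.886 | 0.899-0.905 | 0.018-0.022 | 0.040-0.042 | 0.048-0.051 |
| 6 | 0.887-0.890 | 0.914-0.921 | 0.026-0.031 | 0.035-0.040 | 0.048-0.052 |

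Monte Carlo error for a type I rate is about √(0.05 × 0.95/20,000) = 0.0015. With the overall rates held fixed, the treatment odds ratio within strata rises from 2.05 (readiness OR 1) to between 2.25 and 2.33 (readiness OR 6). The covariate list therefore also affects which odds ratio is being estimated.

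**3. What the selection rule does.** With k independent baseline tests at 0.05, the chance of at least one false imbalance is 1 − 0.95^k: 23% for 5, 40% for 10, 64% for 20. The protocol does not give k.

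A second simulation used block randomisation within readiness, plus site, past EBT use and 10 pure-noise variables (4,000 runs per setting). In four settings the rule selected the stratum in 0 of 4,000 runs each time, and site and past EBT use in about 5% of runs each.

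| ORs (readiness, site, past use) | Power: rule | Power: prespecified three | Type I: rule | Type I: prespecified |
|---|---|---|---|---|
| 2, 1.3, 2 | 0.849 | 0.865 | 0.048 | 0.050 |
| 3, 1.5, 3 | 0.829 | 0.871 | 0.048 | 0.056 |

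Here 2.05 is the conditional odds ratio, so only the differences should be read, not the levels against 0.87. The gains are 1.6 and 4.2 points. Monte Carlo error for type I is √(0.05 × 0.95/4,000) = 0.0034. The 0.056 lies 1.7 such errors above 0.05, so the 4.2 may be slightly generous.

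**The case against.** The strongest reply is that little is lost and nothing is invalid. Age, gender and race/ethnicity are fixed in advance; only the additions are chosen by testing. The rule looks at arm and baseline data, not outcomes, so it does not let anyone choose the model that gives the best result. A separate simulation of the rule supports this. It used 364 participants, 20 independent candidate variables of which two were mildly prognostic, and 4,000 runs per setting. For readiness odds ratios of 1, 2, 3 and 6, type I error was 4.3%, 5.3%, 4.6% and 3.5%, against 4.2%, 5.1%, 4.4% and 3.8% with no covariates. All of this stands.

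It also stands that:

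- the gains rest on assumed odds ratios and vanish if readiness does not predict EBT use;
- site is not a stratum, so adjusting for it is an efficiency choice, not a requirement of the design;
- the 64% needs 20 independent tests, and real baseline items are likely to be correlated;
- attrition could disturb the stratum's balance slightly, so the 0 of 4,000 describes the blocked design rather than the retained sample;
- six covariates may be too many for verified abstinence, since sections 2.1 and 3 expect low quit rates.

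Section 9.4.1 promises a formal SAP before unblinding, where the list could be settled. That is an opportunity rather than an answer, because the protocol already states the selection rule outright.

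**Conclusion.** The point holds as a matter of efficiency and prespecification. The stratum is absent from every primary and secondary main-effect model, and the rule for adding covariates will in practice not bring it in. The size is about 0 to 3 power points for the stratum alone, and up to about 4 with site and past EBT use, over the assumed odds ratios and 20-60% ready. The omission and the open-ended covariate list are plain from the text and need no assumption.

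A reader might infer more than the protocol supports:

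- **Inflated false positives.** The checks show the opposite direction: type I error falls to about 0.035-0.049 when a prognostic stratum is left out.
- **An underpowered trial.** The 0.87 is for an unadjusted chi-square test and does not depend on adjustment.
- **A wholly data-driven model.** Three covariates are named in advance.
- **Readiness ignored altogether.** It is in the moderator models, although those do not supply the main treatment estimates.

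This is a worthwhile, low-cost correction rather than a threat to the trial's validity.

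**What to change.** In the models for Hypotheses 1 to 3 (9.4.1 to 9.4.3), replace the significance-based clause with a fixed list: readiness stratum as randomised, site, baseline past EBT use, age, gender and race/ethnicity. Remove the significance trigger from 9.4.5 and keep the baseline table descriptive; this also settles the disagreement with 9.4.2. For verified abstinence, allow a prespecified smaller set that keeps at least the stratum, with the condition for using it (for example, a minimum number of events) written down before unblinding.

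The SAP should say which readiness assessment defines the stratum, because sections 1.1 and 4.1 describe both a baseline and a clinic-day assessment. It should also note that the adjusted odds ratio is conditional on the listed covariates.

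The cost is wording in the protocol and SAP. Site and the stratum are known at randomisation, and past EBT use is on the baseline questionnaire, so no new data or participants are needed.

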#### 9.4.3 ANALYSIS OF THE SECONDARY ENDPOINT(S)

Aim 1 Hypothesis 1.2. Dose of EBT utilization. As a secondary outcome, we will examine the total number of EBTs contacted over the 7-month study period (ranging from 0 to 4, for the quitline, any clinic-based program, NCI's text message program, and nicotine replacement or other medication). Participation in the Quitline or NCI's text message program will be based on usage data from the programs. Participation in clinic-based programs or use of smoking cessation medication outside of the quitline will be based on self-report. The number of EBTs utilized will be analyzed through Poisson regression for count data, with the intervention effect described through a rate ratio and 95% confidence interval describing the increased probability of engaging in an additional EBT for those in the Intervention vs. Control. We will control for age, gender, race/ethnicity, and variables identified through preliminary analyses as significantly differing between study groups.

Aim 1 Hypothesis 1.2. Dose of EBT utilization. As a secondary outcome, we will also create a binary indicator of use of a combination of counseling (including quitline, clinic-based programs, and the NCI's text message program) and medications over the 7-month study period. The Intervention will be compared to Control on this outcome through logistic regression, with the intervention effect summarized through an odds ratio and 95% confidence interval. We will control for age, gender, race/ethnicity, and variables identified through preliminary analyses as significantly differing between study groups.

Aim 2. Quit attempts and motivation to quit, and Aim 3. Biochemically verified abstinence. Dichotomous data on quit attempts, motivation to quit, and biochemically verified abstinence will be collected at one-month post-appointment (the end of the text message program), and at 3 and 6 months follow-up. Data on quit attempts will be based on the question "Since last contact, how many times have you stopped smoking for at least 24 hours because you were trying to quit smoking (not due to illness/hospitalization)?" Our main analyses for this outcome will examine the dichotomized outcome of 'any quit attempt', although we will collect data on the number of attempts and duration. Motivation to quit will be based on the question "Are you seriously thinking of quitting smoking in the next 30 days (yes or no)?" To determine point-prevalence abstinence, participants will be asked "In the last 7 days, have you smoked any cigarettes at all, even a puff?" For those responding 'no', biochemical verification will be implemented with salivary cotinine, with abstinence defined as cotinine values < 15 ng/mL. If participants indicate use of Nicotine Replacement Therapy or electronic nicotine delivery system use, these data will be recorded and reported separately from cotinine-validated abstinence. For these outcomes, the Intervention will be compared to the Control on data from 1-month post-appointment and at 3 and 6 month follow-up through mixed effect logistic regression models with random intercepts for longitudinal dichotomous data. These models will include indicator variables for intervention group, time, and interaction between intervention group and time (which will model and test whether changes in motivation to quit follows different patterns over time in the

Based on the NIH Behavioral and Social Intervention Clinical Trial Protocol Template v3.0 - 20180827

Intervention vs. Control group). Intervention effects will be described through odds ratios and 95% confidence intervals. In the case of significant intervention by time interaction, separate odds ratios will be given for intervention effects at each time point. We will control for age, gender, race/ethnicity, and variables identified through preliminary analyses as significantly differing between study groups.

---

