#### **Time 1:** Dental clinic appointment

- At the dental clinic appointment, all participants will be rescreened to confirm smoking status. Those who self-report no smoking in the past 7 days will be terminated.
- Consented participants who do not complete the baseline questionnaire before the start of their dental appointment will also be terminated if a new dental appointment is not scheduled within 45 days of the date they completed screening.

Endpoints and outcome measures:

- Evidence-based treatments (EBTs) for smoking cessation (assessed at Time 4 – 6). The EBTs for smoking cessation that will be assessed are: 1) the state quitline (operated by National Jewish Health; objective utilization of phone counseling services which also include the number of counseling calls completed, and eligibility for, and provision of, nicotine replacement therapy); 2) the NCI SmokefreeTXT (objective utilization of SmokefreeTXT, the NCI text-message program for smoking cessation, which also includes length of program utilization, and program engagement); 3) clinic-based cessation services (self-report utilization of smoking cessation

counseling, either individual or group sessions, offered by community health centers, hospitals or clinics, which also includes the number of sessions attended, and the provision and use of pharmacologic treatments); 4) pharmacologic treatment (utilization of nicotine replacement therapy products such as the nicotine patch, gum or lozenge, and the nicotine spray or inhaler, and non-nicotine medications such as Zyban, Wellbutrin or Bupropion, Chantix or Varenicline, obtained through physician prescription or, in the case of nicotine replacement products, through the quitline or purchased by participants). Depending on the method of pharmacologic treatment acquisition, pharmacologic treatment utilization may be objective or self-report. Acquisition of nicotine replacement therapy will be verified if participants receive them from the state quitline.

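### Section 9.4.3 plans plain Poisson regression for the 0–4 EBT count with no robust variance or dispersion check, and describes the rate ratio as a probability

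*Combined protocol and SAP*

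**What the plan says.** Section 9.4.3 defines the outcome as "the total number of EBTs contacted over the 7-month study period (ranging from 0 to 4"), the four items being the quitline, any clinic-based program, the NCI text program, and nicotine replacement or other medication. On the model it says "The number of EBTs utilized will be analyzed through Poisson regression for count data". The result is to be a rate ratio with a 95% confidence interval, "describing the increased probability of engaging in an additional EBT for those in the Intervention vs. Control", adjusted for age, gender, race/ethnicity and any variables found to differ between the groups.

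The section does not say how the standard error is obtained. The only distributional check in the plan, in Section 9.4.1, is for the utilization index score. Section 9.4.1 also promises a formal SAP before unblinding.

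The share of participants with a non-zero count comes from the power calculation in Section 9.2: "corresponding to percent with any EBT utilization of 22.7% in the Control vs. 37.6% in the Intervention". No section says how many EBTs a user is expected to contact.

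**The concern.** A Poisson model with model-based errors takes the variance of the count to equal its mean. This outcome is a bounded sum of four yes/no items, and its variance depends on how strongly use of one EBT goes with use of another. If users tend to take up several, the variance exceeds the mean, the interval is too narrow and the test rejects too often. If users take up only one each, the reverse holds.

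Three statements point towards clustering of use. The endpoint table in Section 3 says participants will be encouraged to use more than one EBT. Section 6.1.1 says both smoking cessation videos stress combining behavioral strategies with medication. Section 8.1 lists nicotine replacement obtained through the quitline under pharmacologic treatment, although the quitline is a separate EBT, and adds: "Acquisition of nicotine replacement therapy will be verified if participants receive them from the state quitline". A single quitline contact could therefore count towards two items.

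The count is called secondary in Section 9.4.3 but appears under the primary endpoint in Sections 1.1 and 3, and Section 9.2 rules out multiplicity adjustment. A poorly calibrated test here has no other safeguard.

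The description of the rate ratio raises a second problem: a reader told that it is a change in probability would misread the result.

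**Working it through.** **Inputs.** Any EBT use is 22.7% in Control and 37.6% in Intervention, with 364 analysed (182 per arm) and a two-sided 5% level (Sections 9.2 and 9.4.1). The distribution of the number of EBTs among users is an assumption throughout.

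**The plan's own figure.** Section 9.2 states "364 subjects (455 minus 20% lost to follow-up or ineligible post-randomization), we will have 0.87 power to detect the anticipated effect". A two-proportion calculation with 182 per arm gives 0.875, and 455 × 0.8 = 364. The inputs therefore reproduce. The plan gives no power or dispersion figure for the count itself.

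**Formula.** Let p be the share with any use, and K the number of EBTs contacted among users. The count has mean μ = p·E[K]. Its variance-to-mean ratio is

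φ = E[K²]/E[K] − p·E[K].

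Under the null with n per arm, the model-based variance of the log rate ratio is about 2/(nμ), while the true variance is φ times that. The Wald statistic therefore has variance φ, and

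type I error = 2·[1 − Φ(1.96/√φ)].

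**Example.** Users split 50/30/15/5% over 1, 2, 3 and 4 EBTs, with p = 0.227.
- E[K] = 0.50 + 0.60 + 0.45 + 0.20 = 1.75
- E[K²] = 0.50 + 1.20 + 1.35 + 0.80 = 3.85
- φ = 3.85/1.75 − 0.227 × 1.75 = 2.20 − 0.40 = 1.80
- 1.96/√1.80 = 1.46, so type I error = 14.4%

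**Results.** The second pair of columns uses the average of the two arms, (22.7 + 37.6)/2 = 30.15%.

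| Assumed use among users | φ, p = 22.7% | Type I error | φ, p = 30.15% | Type I error |
|---|---|---|---|---|
| All contact one | 0.77 | 2.6% | 0.70 | 1.9% |
| Four independent, equally likely EBTs | 0.94 | 4.3% | 0.91 | 4.0% |
| 20% contact exactly two, rest one | 1.06 | 5.7% | 0.97 | 4.7% |
| 50% contact exactly two, rest one | 1.33 | 8.9% | 1.21 | 7.5% |
| 70/20/8/2 over 1–4 | 1.47 | 10.6% | 1.36 | 9.3% |
| 50/30/15/5 | 1.80 | 14.4% | 1.67 | 13.0% |
| 40/30/20/10 | 2.05 | 17.1% | 1.90 | 15.5% |

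For the independent case, each EBT has probability 1 − 0.773^(1/4) = 0.062, so φ = 1 − 0.062 = 0.94.

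**Where the direction changes.** If users contact only one or two EBTs and a share s contact two, φ = 1 when 2s = p(1 + s)². That gives s of about 15% at p = 22.7% and about 23% at p = 30.15%.

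**Simulation.** For the all-one split and the three splits over 1–4 in the table, 40,000 simulated trials each at 182 per arm agreed with the formula to within about 0.6 percentage points. With sandwich errors on the same model, type I error was 4.7% to 5.2% across all unadjusted scenarios. In covariate-adjusted fits (2,000 per scenario) it was 4.6% to 5.8%. The Monte Carlo standard error of those fits is about √(0.05 × 0.95/2000) = 0.5 percentage points.

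**The rate ratio.** It equals (p_I/p_C) × (E[K_I]/E[K_C]). On the plan's rates the ratio of probabilities of any use is 37.6/22.7 = 1.66. The rate ratio equals 1.66 only if users in both arms contact the same mean number. If Control users split 60/25/10/5 (mean 1.6) and Intervention users 40/30/20/10 (mean 2.0), it is 1.656 × 2.0/1.6 = 2.07, with the probabilities of any use unchanged.

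**The case against.** The strongest reply is that the plan never says the errors will be model-based. It names a model and is silent on the variance estimator, and a formal SAP is still to come. This is correct. Model-based errors are the usual software default, but their use here is an inference, so a reader should not conclude that the planned intervals are wrong. What stands is that the choice is open and one of the two obvious options is unsafe.

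A reader might also infer that 77.3% zeros in Control already rules out a Poisson model. It does not: a Poisson variable with mean 0.257 has exp(−0.257) = 77.3% zeros. Only the variance-to-mean ratio matters, and the documents do not give it.

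Nor should the table be read as a bound or a forecast. Near-independent use gives about 4%. An even split over one to four EBTs gives about 19% to 21%. The documents do not fix even the direction. The dual listing of quitline-supplied nicotine replacement makes double counting plausible, but no scoring rule states it.

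Finally, Section 9.4.3 correctly calls the estimate a rate ratio, and only the explanation attached to it is wrong. That makes it a small error to correct, but still an error.

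**Conclusion.** The concern holds in conditional form. The variance estimator for the EBT count is unspecified, with no dispersion check or fallback. If model-based Poisson errors are used, the type I error of a nominal 5% test runs from about 2% to 17% over the splits tabulated, depending on how many EBTs users contact. Those splits are assumptions. Overdispersion, with intervals too narrow, is more likely than underdispersion because combined use is encouraged and the quitline supplies nicotine replacement.

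The description of the rate ratio as an increased probability is wrong whatever the distribution. The logistic analysis of any EBT use, on which the sample size in Section 9.2 is based, is not affected. Whether the count is primary or secondary needs reconciling separately and bears on how much weight this point carries.

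**What to change.** In the SAP, and preferably in Section 9.4.3:

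- Keep the log-linear (Poisson) mean model with the planned covariates.
- State that the test and 95% confidence interval use robust (sandwich) standard errors. This works whether the variance is above or below the mean, so no data-dependent choice between models is needed.
- Describe the estimate as the ratio of the mean number of EBTs used, Intervention to Control, and remove the reference to probability.

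The cost is a sentence or two of text and one software option. No change to data collection or sample size is needed, and it can be done before unblinding.
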